7.7 Analysis of Roll-In Subjects

Descriptive statistics will be presented for all Wave II endpoints for subjects in the Roll-in analysis set, separately.

8 DATA MONITORING COMMITTEE

A Data Monitoring Committee (DMC) will assess subjects' data for safety on regular intervals for Wave I and Wave II and make recommendations on study adaptations as described in the DMC Charter. An independent statistician will be responsible for conducting the interim analyses and reviewing the results with the designated DMC. The DMC charter will document the constitution, roles and responsibilities of the committee, sponsor, and the independent statistician.

10 APPENDIX I – ADAPTIVE DESIGN SIMULATION REPORT

10.1 Study Design

This clinical investigation is a prospective, non-randomized, pre-market clinical evaluation of the IRE system (circular IRE catheter and IRE generator) to demonstrate safety and long-term effectiveness when compared to an historical performance goal. The sample size for the study is primarily driven by the effectiveness endpoint. A Bayesian adaptive design will be used to determine the sample size based on the effectiveness endpoint. A single Bayesian interim analysis for early success will be performed when 30 subjects full follow-up of one year and all subjects in the mITT analysis set complete 3 months of follow-up. The final analysis will use a beta-binomial model after all subjects complete the 12 months follow-up.

The effectiveness endpoint will be assessed by testing the hypotheses:

$$H_0: p_E \leq 0.50 \quad \text{vs.} \quad H_A: p_E > 0.50,$$

where p_E is the proportion of patients free from effectiveness events.

Let X be the number of patients that are failure-free through 12 months. We model the number of patients free from an event as

$$X \sim \text{Binomial}(n, p_E),$$

where n is the number of patients. We use a vague Beta(1, 1) prior distribution for p_E . Then the posterior distribution is

$$(p_E | x, n) \sim \text{Beta}(1 + x, 1 + n - x).$$

Similarly, the hypothesis test for the safety endpoint is:

$$H_0: p_S \geq 0.14 \quad \text{vs.} \quad H_A: p_S < 0.14,$$

where p_S is the rate of the Primary Adverse Events (PAEs). We model the number of patients with PAEs as

$$Y \sim \text{Binomial}(n, p_S)$$

with a vague Beta(1, 1) prior distribution on p_S .

The trial will be considered a success at the time of the final analysis if BOTH

1. $\Pr(p_E > 0.5 | x, n) > 0.9775$ AND
2. $\Pr(p_S < 0.14 | y, n) > 0.975$.

These thresholds control the overall Type I error rate for the trial below one-sided 2.5%.

10.2 Sample Size Justification

The methods described in Broglio et al.¹ will be used to determine the sample size based on the effectiveness endpoint. Sample size selection interim analyses will be performed when 180 and 255 patients are enrolled in the mITT analysis set. Predictive probabilities for trial success will be used to determine whether the sample size at the time of the interim analysis will be sufficient or

if the trial will continue to the full sample of 330. The power for testing the primary safety endpoint is greater than 80% at all sample sizes greater than or equal to 180 subjects, assuming a primary safety rate of 7% with a performance goal of 14%.

It is assumed that there is a 5% dropout rate for the safety endpoint and a 15% dropout rate for the effectiveness endpoint. The sample size will provide greater than 80% power at one-sided significance level of 2.5% for each endpoint assuming that a true safety rate of 7% and a true effectiveness rate of 65% compared to the performance goals of 14% and 50% respectively.

10.3 Adaptive Sample Size Determination

Sample size selection interim analyses will be performed when 180 and 255 subjects (excluding roll-in) are enrolled in the mITT analysis set. Predictive probability of success for the effectiveness endpoint will be used to determine whether the sample size at each interim analysis will be sufficient or if the trial enrollment will continue. Sample size simulations were performed using performance goals of 14% and 50% respectively for the safety and effectiveness endpoints.

At the time of each interim analysis, predictive probability of success for the effectiveness will be calculated once using the current sample size and another time using the maximum sample size allowed. If the effectiveness predictive probability is greater than 90%, or if the effectiveness predictive probability with the maximum sample size of 330 is less than 2.5%, then the enrollment will be stopped. Otherwise the enrollment will continue.

10.3.1 Prediction Probability for the Effectiveness Endpoint

To estimate the predictive probability of success for the effectiveness endpoint at each interim analysis, time-to-failure during the 9-month (39 weeks) post-blanking period will be modeled by a piecewise exponential model with 3 distinct intervals (from (0, 2], (2, 8], and (8, 39] weeks). The three-piece exponential model provides a reasonable amount of flexibility in capturing the functional form of the survival function for the effectiveness endpoint.

A vague Gamma prior distribution will be assumed for estimating each of the hazard rates:

$$h_j \sim \Gamma(\alpha=0.1, \beta=0.1) \text{ for } j = 1, 2, 3.$$

where α represents the prior number of events and β the prior exposure time. At the sample size selection interim analysis with n enrolled patients, the total number of observed events for time interval j is EV_j and the total observed exposure time for time interval j is EXP_j , assuming each patient i offers EXP_{ij} exposure for time period j . For each time interval, we update the prior distribution with the currently observed data (EV_j, EXP_j) and the resulting posterior distribution is:

$$h_j \sim \Gamma(\alpha + EV_j, \beta + EXP_j).$$

The predictive probabilities of trial success will be calculated using Monte Carlo integration. For the predictive probability of trial success at the current sample size, we assume accrual is stopped and the primary analysis is conducted after all subjects complete the 12 months follow-up. The data will be imputed in the following fashion. First, a single hazard rate, h_j , is sampled from the posterior distribution of the hazard rates for each time interval. For each patient who has not yet experienced an event, depending on which time interval their current observed time falls in, we sample an event time from an exponential distribution with mean equal to the sampled hazard rate for that time interval:

$$TTE_{ij} \sim \text{Exponential}(h_j),$$

where TTE_{ij} represents the time to event for patient i in time period j . For patient i , his or her imputed exposure time for time interval j would be $EXP_{ij} + TTE_{ij}$. If the imputed exposure time is less than or equal to the end of the time interval, the patient will be considered an event, otherwise, the sampled h_j for the next time interval will be used to generate a time for the next time interval and impute the exposure time. The patient time will be censored at 39 weeks if the imputed time for the last time interval is greater than 39 weeks. Additionally, a censoring time will be sampled from an exponential distribution with a rate that results in the assumed attrition rate for the effectiveness endpoint at 1 year. If this censoring time is less than the event time for the subject, then the patient will be censored at this time and will not count as an event.

This process will be repeated 1000 times to generate 1000 imputed datasets. For each of these imputed datasets, success of the final analysis for the effectiveness endpoint will be assessed once assuming we would stop at the interim with the current sample size and another time assuming we use the maximum sample size of 330. The proportion of successful trials in each case provides the predictive probability of success for the effectiveness endpoint.

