7.4.2 Primary Effectiveness Endpoint

The primary effectiveness endpoint is defined as freedom from documented (symptomatic and asymptomatic) atrial arrhythmia (atrial fibrillation [AF], atrial tachycardia [AT] or atrial flutter

[AFL]) recurrence based on electrocardiographic data (≥ 30 seconds on arrhythmia monitoring device) during the effectiveness evaluation period (Day 91-Day 365). Acute procedural failure (i.e., failure to confirm entrance block in all PVs except those that are silent and/or cannot be cannulated post-procedure, use of a non-study catheter for PV isolation, or failure to have PFA delivery with the study catheter due to IRE system malfunctions) will also be considered a long-term effectiveness failure. Subjects without effectiveness failure who undergo a repeat ablation procedure during the blanking period where PVs were ablated with a commercially available catheter and generator will be considered non-assessable for long-term effectiveness of the IRE ablation system and thus will be excluded from this analysis. The primary analysis of the primary effectiveness endpoint will be performed in the PP analysis set.

The primary effectiveness endpoint will be assessed by testing the following hypothesis:

$$H_0: p_E \leq 0.50 \quad vs \quad H_A: p_E > 0.50 ,$$

Where p_E is the effectiveness success rate.

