7.4.2.1 Early Success Interim Analysis of Primary Effectiveness Endpoint

At the time of the early success interim analysis, the primary effectiveness endpoint will be met if:

$$\Pr(p_E > 0.50 | x, n) > 0.9975$$

where p_E is the effectiveness success rate. If the posterior probability of the effectiveness success rate being greater than 50% is greater than 0.9975 then the study will be considered to have demonstrated effectiveness of the device at the early success interim analysis.

At the time of the early success interim analysis, the time-to-failure during the 9-month (39 weeks) post-blanking period will be modeled by using a piecewise exponential model. The model will consist of three distinct time intervals during the 9-month evaluation period: (0, 2], (2, 8], and (8, 39] weeks. Failure times during each time interval is assumed to be exponentially distributed with a different hazard rate in each segment. The model is:

$$f(t) = \exp(-th(t))$$

where

$$h(t) = \begin{cases} \lambda_1 & 0 < t \leq 2 \\ \lambda_2 & 2 < t \leq 8 \\ \lambda_3 & 8 < t \leq 39 \end{cases}$$

Vague Gamma prior distributions will be assumed for λ_1 , λ_2 , and λ_3 . Given hazard rates λ_1 , λ_2 , and λ_3 , the failure-free rate at 12 months (9 months post-blanking) p_E can then be estimated

by

$$p_E = \exp(-[2\lambda_1 + (8 - 2)\lambda_2 + (39 - 8)\lambda_3])$$

At the interim, the total number of primary effectiveness events and the total subject exposure time will be used to update the vague Gamma prior and obtain the posterior Gamma distribution for each segment. Then 10,000 random hazard rates will be sampled from the posterior distribution for each segment and each triplet set of hazard rates will be used to calculate p_E . The distribution of p_E is estimated based on the 10,000 calculated p_E s. If the probability of p_E being greater than 50% is greater than 0.9975 (99.75%), the trial will declare early success.

To investigate the robustness of the analysis result, the following sensitivity analyses will be performed in the mITT and PP analysis sets at the time of the early success interim analysis with the available data:

- **Sensitivity to Analysis Set**

The primary effectiveness endpoint will be analyzed in the mITT analysis set as a sensitivity analysis.

- **Kaplan-Meier Analysis**

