10.5 Modeling for Effectiveness

For the effectiveness endpoint, the time-to-failure during the 9-month (39 weeks) post-blanking period is modeled by using a piecewise exponential model. The model has three distinct time intervals: (0, 2], (2, 8], and (8, 39] weeks. These intervals are based on a model fit to the ThermoCool Pivotal trial and the SmartTouch IDE trial. The three-piece exponential model

provides a reasonable amount of flexibility in capturing the functional form of the survival function for the effectiveness endpoint.

For the model-based approach, failure times during each interval is assumed to be exponentially distributed, with different hazard rates in each segment. The model is:

$$f(t) = \exp(-th(t)),$$

where

$$h(t) = \begin{cases} h_1 & 0 < t \leq 2; \\ h_2 & 2 < t \leq 8; \\ h_3 & 8 < t \leq 39. \end{cases}$$

A vague Gamma(1, 1) prior distribution will be used for each h in the model. Given hazard rates h_1, h_2 , and h_3 , the failure-free rate at 12 months p_E can then be estimated by $p_E = \exp(-[2h_1 + (8 - 2)h_2 + (39 - 8)h_3])$.

At the time of the early success interim analysis, the total number of primary effectiveness events and the total subject exposure time will be used to update the vague Gamma prior and obtain the posterior Gamma distribution for each segment. Then 10,000 random hazard rates will be sampled from the posterior distribution for each segment and each triplet set of hazard rates will be used to calculate p_E . The distribution of p_E is estimated based on the 10,000 calculated p_E s. If the probability of p_E being greater than 50% is greater than 0.9975(99.75%), the trial will declare early success.

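### The interim effectiveness models do not say how Day 0 acute failures enter a post-blanking clock, and the likelier reading raises the expected sample size

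*SAP*

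**What the plan says.** The Wave II SAP addresses this in four places.

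- **Endpoint (7.4.2).** Needing another catheter to isolate the veins, or a system malfunction that prevents PFA delivery, is an acute failure. So is the first item in the definition: "Acute procedural failure (i.e., failure to confirm entrance block in all PVs except those that are silent and/or cannot be cannulated post-procedure". Each of these "will also be considered a long-term effectiveness failure". All three are known on the day of the index procedure.
- **Sample-size looks at 180 and 255 subjects (10.3.1).** "time-to-failure during the 9-month (39 weeks) post-blanking period will be modeled by a piecewise exponential model with 3 distinct intervals". On the prior, the section says "A vague Gamma prior distribution will be assumed for estimating each of the hazard rates", namely Gamma(0.1, 0.1). It is updated with the events EV_j and exposure EXP_j that fall in interval j.
- **Early-success look (7.4.2.1 and 10.5).** "the time-to-failure during the 9-month (39 weeks) post-blanking period will be modeled by using a piecewise exponential model", and "the total number of primary effectiveness events and the total subject exposure time will be used to update the vague Gamma prior". Section 10.5 gives the prior: "A vague Gamma(1, 1) prior distribution will be used for each h in the model". The success rate is p_E = exp(-[2h1 + 6h2 + 31h3]), with no other term.
- **Simulations (10.6.1).** Every failure is generated from the same three post-blanking hazards, calibrated to the overall failure-free rate.

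The intervals are (0,2], (2,8] and (8,39] weeks after blanking. Day 0 lies in none of them. The Kaplan-Meier sensitivity analysis in 7.4.2.1 expressly includes acute failure and runs from the initial ablation. The model text does neither.

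**The concern.** The two descriptions pull in different directions. Updating with all primary effectiveness events (7.4.2.1) suggests that acute failures are counted. Updating with events inside each interval (10.3.1) leaves them with nowhere to go.

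If they are counted in the first interval, the look at 180 subjects sets failures from all enrolled subjects against exposure from the part of the cohort already past Day 90. Event-free subjects still in blanking are known acute successes, yet they are imputed with a hazard that includes a risk they have already passed. The model is then too pessimistic, and enrolment continues more often than it needs to.

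If they are left out, p_E becomes success given acute success, which is higher than the stated endpoint. This matters most at the early-success look. The Protocol summary ties early success to filing for the CE Mark while follow-up continues, and the later effectiveness analysis is then descriptive (Protocol 20.4.4.3; SAP 7.4.2.2).

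**Working it through.** **Inputs.** True rate and goal: "a true effectiveness rate of 65% compared to the performance goals of 14% and 50% respectively" (10.2, effectiveness 65% against 50%). Realistic enrolment from Table 1; hazard ratios 38.06 : 1.71 : 1 (10.6.1); 15% dropout per year (10.6.2); stopping rules of 90% and 2.5% predictive probability; early-success threshold 0.9975; final threshold 0.9775 with Beta(1,1). The documents give no acute-failure rate a, so 2%, 5% and 10% are assumed.

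**Reproducing the plan.** Table 2 at 0.65 has hazards 0.1397, 0.0063 and 0.0037. Then 2(0.1397) + 6(0.0063) + 31(0.0037) = 0.4319, and exp(-0.4319) = 0.649. Table 3.a implies a mean N of 180(0.5535) + 255(0.2854) + 330(0.1611) = 225.6, with Win Effect 0.9457. A simulation of the design gave mean N 220.7 and Win Effect 0.960 when imputed dropouts are kept as non-events. Excluding imputed dropouts gave 257 and 0.978, so the first variant is used below.

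**Counting, by hand (N=180, a = 5%).**
- Acute failures: 180 x 0.05 = 9.
- Subjects past Day 90 (SAP section 6): 30% + 18% + 2% = about 50%.
- Post-blanking success among acute successes: 0.65/0.95 = 0.684, so 2h1 + 6h2 + 31h3 = 0.379 and h1 = 38.06 x 0.379/117.38 = 0.123. Here 117.38 = 2(38.06) + 6(1.71) + 31.
- The simulated posterior mean of h1 goes from 0.124 to 0.190 when the 9 failures are added. This implies 9/0.066 = about 136 subject-weeks of first-interval exposure.
- With h1 = 0.190: 2(0.190) + (0.379 - 2(0.123)) = 0.513, and exp(-0.513) = 0.60, against a true 0.65.
- Put differently, the acute component is charged as exp(-2 x 0.066) = 0.876 instead of 0.95.

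**Counting, simulated at a true 65%.**

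| Assumed a | 2% | 5% | 10% |
|---|---|---|---|
| Model p_E at N=180, counted | 0.630 | 0.602 | 0.550 |
| Model p_E at N=180, separate term | 0.648 | 0.649 | 0.647 |
| Stop at 180, separate term | 59% | 59% | 61% |
| Stop at 180, counted at once | 53% | 43% | 28% |
| Mean N, separate term | 219 | 219 | 218 |
| Mean N, counted once past Day 90 | 223 | 229 | 240 |
| Mean N, counted at once | 226 | 239 | 259 |

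The probability of winning on effectiveness did not fall: at 5% it was 0.957 with a separate term and 0.970 when counted at once. With imputed dropouts excluded, the direction for N is the same (5%: 255 to 277). In that variant, which does not match the plan, the win probability at 10% fell from 0.972 to 0.947.

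At the early-success look, counting is mildly conservative: mean p_E is 0.478, against 0.484 with a separate term (true 0.50, a = 5%, N=180).

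**Omitting, at the early-success look.** The model estimates p_E/(1-a). A true 0.50 is read as 0.50/0.98 = 0.510, 0.50/0.95 = 0.526 or 0.50/0.90 = 0.556, before shrinkage by the prior. The nominal false early-success rate is 1 - 0.9975 = 0.25%.

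| Assumed a | 2% | 5% | 10% |
|---|---|---|---|
| False early success, fixed N=180 | 0.15% | 0.62% | 2.6% |
| False early success, fixed N=330 | 0.38% | 1.15% | 7.0% |

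With a separate term it is about 0.05-0.14%.

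**Not reproduced.** The share stopping at 180 (0.58 against 0.5535), the Early Success column (0.76 for effectiveness alone against 0.8316) and the 1.68% effectiveness type I error (about 0.3-0.5%, few trials). Differences between handlings are therefore firmer than absolute levels.

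**The case against.** The strongest reply is that this is a missing sentence and not a demonstrated bias. The wording of 7.4.2.1 and the companion Kaplan-Meier analysis both favour counting. The branch that threatens a false claim is therefore the weaker reading, and under counting the early-success look is off by only 0.6 points, in the conservative direction. The final beta-binomial test uses observed 12-month outcomes and scores acute failures correctly. All of this stands, and it limits the point.

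A second reply is that few acute failures may reach the model. The SAP per-protocol set (5.1) requires ablation with the IRE system, which removes subjects with no PFA delivery. The Protocol per-protocol set (20.3.2) also removes subjects who needed a non-study catheter for PVI, and Protocol 8.2.1 accepts entrance block reached with touch-up. This also stands, but it shows that the number of affected subjects depends on definitions that the two documents do not share.

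A third reply is that the 38-fold first-interval hazard may already absorb early failures. The documents do not say. Even if it does, it would not represent failures known for the whole cohort while about half is still in blanking.

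Acute failures might also be scored directly and kept out of the hazards. That would largely cure the sample-size looks, but no text selects it, and the early-success rate would still come from the hazards alone.

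**Conclusion.** The rule for Day 0 failures is unspecified, and under either reading at least one interim look does not estimate the stated endpoint. On the better-supported reading the cost is expected sample size. Mean N rises by about 4-7 subjects at 2% acute failure, 10-20 at 5% and 22-41 at 10%; the lower figure in each pair applies if failures enter only once a subject passes Day 90. N cannot exceed 330, and no power was lost in the variant that matches the plan.

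On the less supported reading, false early success at a true 50% is about 0.15-0.38% (2%) or 0.6-1.2% (5%), against a nominal 0.25%. A reader might infer that overall type I error exceeds 2.5%, especially from the figures at 10%. That is not shown. Those figures use fixed sample sizes, an assumed high rate and the weaker reading. Type I error for the whole adaptive trial was not computed under either handling, and the plan's own type I figure was not reproduced. Equally, the SAP's simulations give no reassurance here, because they test neither handling.

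Every size above rests on an assumed acute-failure rate. At 2% the effect is small. The point merits a change to the SAP but does not put the final analysis in doubt.

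**What to change.** At both sample-size looks and the early-success look, model acute failure separately:

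- a ~ Beta(1 + acute failures, 1 + treated - acute failures), from all treated subjects in the analysed set;
- estimate and impute the piecewise hazards among acute successes only, scoring enrolled acute failures as failures and drawing acute status first for subjects not yet enrolled;
- p_E = (1-a) x exp(-[2h1 + 6h2 + 31h3]).

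In the simulation this kept mean N at 218-219 for a between 2% and 10%.

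Reconcile the per-protocol definitions in Protocol 20.3.2 and SAP 5.1, since they decide how many acute failures enter the model. Rerun the Appendix I simulations over a range of acute-failure rates that includes low values, and report power, expected N and type I error for each.

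Cost: SAP wording, a few lines of code and one simulation re-run.

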10.4 Interim Analyses for Early Success

One interim analysis is planned for an early success claim. The interim analysis will be performed when the first 30 subjects complete full follow-up of one year and all subjects in the MITT analysis set complete 3 months of follow-up. For the safety endpoint, the outcome for all patients will be known at the time of this interim analysis and the test will be final primary safety analysis.

At the interim analysis, the trial will declare early success if:

1. The safety objective is met.
2. Posterior probability of the effectiveness proportion p_E being greater than 50% is greater than 0.9975.

The posterior probability is estimated based on the proposed model in the next section.

